3.0 ABBREVIATION

AE	adverse event
BMI	body mass index
CKD	chronic kidney disease
COI	conflict of interest
CRO	contract research organization
DHA	docosahexaenoic acid
EDC	electronic data capture
EPA	eicosapentaenoic acid
FAS	full analysis set
FMD	flow mediated dilation
GCP	Good Clinical Practice
HDL-C	high density lipoprotein-cholesterol
ICH	International Conference on Harmonisation
JAPIC	Japan Pharmaceutical Information Center
LDL-C	low density lipoprotein-cholesterol
MedDRA	Medical Dictionary for Regulatory Activities
PT	Preferred Term
SAS	safety analysis set
sdLDL	small dense low density lipoprotein
SLE	systemic lupus erythematosus
SOC	System Organ Class
TG	triacylglycerol

4.0 INTRODUCTION

4.1 Background

In recent years, metabolic syndrome has been socially concerned, posing multiple risks including for coronary artery disease in association with visceral obesity-induced insulin resistance. Dyslipidemia, characteristically observed, represents a series of abnormal findings including increased TG, decreased HDL-C, sdLDL and remnant cholesterol in the blood. When one becomes highly resistant to insulin, TG increases and LDL quality alters, i.e., sdLDL with particles with small diameters increases. SdLDL is easily engulfed by macrophages and thus may accelerate formation of atherosclerotic plaque. Among other LDL, sdLDL is a small particle with the mean diameter of ≤ 25.5 nm. An overseas report showed 3-fold higher incidence of myocardial infarction in the patient population predominantly having sdLDL.¹⁾ There is another report that sdLDL was found in $\geq 70\%$ of Japanese patients with myocardial infarction²⁾, suggesting importance of measurement of particle sizes of LDL as a part of risk assessment for coronary artery disease.

Given the above situation, especially after LDL-C was successfully lowered with a HMG-CoA reductase inhibitor, it may be important to lower sdLDL in order for further reduction of coronary artery disease risk. Recently, eicosapentaenoic acid (EPA) and docosahexaenoic acid (DHA) that are omega-3 fatty acids have been highlighted as drugs having such activity. EPA and DHA have TG-lowering and antiatherosclerosis activities but the mechanism has not been completely elucidated. Omega-3-acid ethyl esters (an EPA/DHA preparation, Lotriga[®]) released in 2013 lower TG levels in a dose-dependent manner³⁾ and are expected to have the potential to lower RLP, enlarge the LDL particle size, improve FMD, and lower IL-6 levels for example.⁴⁾

The outcomes previously obtained in clinical studies for omega-3-acid ethyl esters indicated that efficacy of the product is comparable to of an EPA-E preparation in hyperlipidemic patients for which an EPA preparation is indicated. However, change and course of LDL-C after administration of omega-3-acid ethyl esters are remain to be elucidated.⁵⁾

In this clinical study, Lotriga[®] (an EPA/DHA preparation) will be administered to hyperlipidemic patients receiving a HMG-CoA reductase inhibitor, and the specific 20-lipoprotein fraction including sdLDL will be assayed with HPLC using gel filtration columns, an established assay for precise analysis⁶⁾, for exploration of “quality of lipids,” i.e., numbers of particles of lipids and lipoprotein in the blood and their change.

4.2 Rationale for the proposed study

This clinical study was planned to explore the effects of omega-3-acid ethyl esters on the lipid and lipoprotein (including sdLDL) profile in the blood in hyperlipidemic patients receiving a HMG-CoA reductase inhibitor for elucidation of “quality of lipids.”

5.0 STUDY OBJECTIVES AND ENDPOINTS

5.1 Objectives

To explore the effects of 8-week treatment with omega-3-acid ethyl esters on the lipid and lipoprotein profile in the blood in hyperlipidemic patients receiving a HMG-CoA reductase inhibitor by use of HPLC in comparison with the control group of patients not treated with omega-3-acid ethyl esters.

5.2 Definition of endpoints

5.2.1 Primary endpoints

Change in mean particle sizes of sdLDL-C and LDL-C in the specific 20-lipoprotein fraction assay

5.2.2 Secondary endpoints

- 1) Change in major lipid constituents in the specific 20-lipoprotein fraction assay
- 2) Change in fatty acids and sdLDL-C in total lipids
- 3) Change in concentration and particle number of lipids, apoprotein and lipoprotein in the blood

5.2.3 Safety endpoints

Adverse events

6.0 CLINICAL STUDY DESIGN

6.1 Clinical study design

<Clinical study design>

This is an multicenter, randomized, open-label study to explore the effects of omega-3-acid ethyl esters on the lipid and lipoprotein profile in the blood in hyperlipidemic patients receiving a HMG-CoA reductase inhibitor in comparison with the control group of patients not treated with omega-3-acid ethyl esters in an unblinded manner by use of HPLC using highly-sensitive gel filtration columns, which is a technique for analyzing lipoprotein.

Considering the factors potentially biasing the lipid and lipoprotein profile in the blood between the treatment groups, study subjects who gave consent and were assessed as eligible in the eligibility assessment will be stratified for allocation by the factors of “fasting TG (< 300 mg/dL or \geq 300 mg/dL) and age (< 65 years or \geq 65 years) at the start of the screening period” (1:1 ratio).

<Treatment>

[1] Study drug

Omega-3-acid ethyl esters

[2] Dosage regimen

The group treated with omega-3-acid ethyl esters: Hyperlipidemic patients receiving a HMG-CoA reductase inhibitor* will orally receive omega-3-acid ethyl esters 2 g immediately after meal twice daily.

The group not treated with omega-3-acid ethyl esters: Hyperlipidemic patients receiving a HMG-CoA reductase inhibitor* will continue to receive the HMG-CoA reductase inhibitor at the same dose regimen as at the time of informed consent.

*: Irrespective of the treatment groups, patients will receive a HMG-CoA reductase inhibitor at a consistent dose regimen that should have been stable for \geq 4 weeks prior to informed consent. Change of the HMG-CoA reductase inhibitor and its dose regimen is not allowed throughout the screening period and the treatment period.

[3] Duration of treatment

8 weeks

<Planned number of study subjects>

50 patients evaluable for the primary endpoint

(25 patients in the group treated with omega-3-acid ethyl esters, 25 patients in the group not treated with omega-3-acid ethyl esters)

<Number of study sites>

Around 5 sites

<Duration of treatment and number of visits for a study subject>

[1] Duration of treatment

The duration of the treatment period is 8 weeks. Visit 1 is to obtain informed consent (Day -29 to Day -1 before the start of study drug administration), Visit 2 is to administer the study drug for the first time (Day -15 to Day -1 before the start of study drug administration), Visit 3 takes place in the 4th week after the start of study drug administration (Week 4), and Visit 4 is to administer the study drug for the last time (Week 8).

[2] Number of visits

Screening period: 1 visit

Treatment period: 3 visits

[figure not shown]
Figure 6 (a) shows an outline of the clinical study design. Refer to Appendix A for schedule of examinations, observations, and evaluations.

Figure 6.a Outline of the clinical study design

<Outline of the clinical study>

Duration of treatment: 8 weeks

Number of visits: 4 visits

(a) by HPLC

6.2 Rationale for the clinical study design

<Rationale>

This clinical study was designed as an open-label study with the control group of patients who will not be treated with omega-3-acid ethyl esters, because the objective is to explore the effects of 8-week, twice-daily, oral treatment with omega-3-acid ethyl esters 2 g on the lipid and lipoprotein profile in the blood in hyperlipidemic patients receiving a HMG-CoA reductase inhibitor. Subjects are to be stratified for allocation (1:1 ratio) by the factors of “fasting TG (< 300 mg/dL or \geq 300 mg/dL) and age (< 65 years or \geq 65 years) at the start of the screening period” that may potentially bias the lipid and lipoprotein profile in the blood, so that the potential bias between the treatment groups is minimized.

<Rationale for the dose regimen>

In accordance with the approved dosage and administration of omega-3-acid ethyl esters, omega-3-acid ethyl esters 2 g is to be orally administered immediately after meal twice daily as the dose regimen in this study. In the Phase 3 confirmatory study in patients with hypertriglyceridemia, superiority of the product 4 g group to the EPA-E group as well as non-inferiority of the product 2 g group to the EPA-E group were confirmed for percentage of change in TG from baseline at the completion of administration of omega-3-acid ethyl esters 2 or 4 g or the control EPA preparation 1.8 g/day. Patients receiving omega-3-acid ethyl esters in actual clinical practice are likely to have increased TG, therefore the dose of 4 g daily was selected as having more marked TG-lowering effect, so that the effects of omega-3-acid ethyl esters on the lipid profiles may be investigated in detail.

<Rationale for the study period>

In the Phase 3 confirmatory study in patients with hypertriglyceridemia, decrease of TG was observed in an early stage (Week 4) after the start of administration with omega-3-acid ethyl

esters 4 g/day, and the product 2 and 4 g/day showed comparable or more marked TG-lowering effect as compared to the control EPA-E preparation 1.8 g/day. For LDL-C, another lipid parameter than TG, decrease was observed since Week 4 after the start of administration with the product 4 g/day. Therefore, the 8-week treatment duration including additional 4-week treatment is set to investigate the effects of omega-3-acid ethyl esters on the lipid profiles in detail in this study. As a result of the Phase 3 confirmatory study, no tendency for LDL-C to increase constantly was observed in association with treatment with the product, while it is still unknown what induced transient LDL-C increase after treatment with the product.

<Rationale for the number of planned study subjects>

See Section 13.3.

6.3 Premature termination of entire clinical study or premature termination of clinical study at a study site

6.3.1 Premature termination criteria of entire clinical study

The sponsor should immediately discontinue the study when at least one of the following criteria is applicable:

- When new information or other evaluation on the safety or efficacy of the study drug becomes available that shows a change in the known risk/benefit profile of the concerned compound, and risks/benefits are no longer tolerable for study subject participation in the study.
- When there is serious deviation from Ethical Guidelines or ICH-GCP for medical and health study involving human subjects.

6.3.2 Criteria for premature termination of study sites

Termination of involvement of a study site in the study may be requested prematurely at the discretion of the sponsor if the entity (e.g., principal investigator) is found to have significant violation of the ethical guidelines, protocol, or contractual agreement for medical and health study involving human subjects or becomes unable to ensure proper conduct of the study, or otherwise as specified in the contractual agreement.

6.3.3 Procedures of clinical study suspension and premature termination of entire clinical study or clinical study at a study site

In the event that the sponsor or a study site committee such as an Ethical Review Board decides to prematurely suspend or terminate the entire clinical study or clinical study at a study site, a study-specific procedure shall be provided by the sponsor. The procedure shall be followed by applicable study sites during the course of clinical study suspension or premature termination.

6.4 Procedures for protocol revision

If the protocol needs to be revised, the sponsor shall consider and decide whether to revise the protocol.

The principal investigator of each study site shall be informed of the details of each protocol revision. Principal investigators shall confirm the content of the revision of the protocol and submit a letter of agreement to the sponsor as evidence of agreement with the protocol revision.

Upon notification, the principal investigator at each study site shall submit the revised contents to committees such as the Ethical Review Board, as necessary according to institutional regulations for review, and obtain approval from the director of the entity.

7.0 SELECTION AND WITHDRAWAL CRITERIA OF STUDY SUBJECTS

The principal investigator or investigator shall check for all the inclusion/exclusion criteria including the test results prior to randomization.

7.1 Inclusion criteria

Eligibility of study subjects shall be determined in accordance with the following criteria.

1. Patients diagnosed as hyperlipidemia.
2. Patients receiving a HMG-CoA reductase inhibitor continuously at a stable dose regimen for at least 4 weeks at the start of observation period at Visit 1 (Day -29 to Day -1 before the start of study drug administration)
3. Patients with fasting TG of ≥ 150 to < 400 mg/dL at the start of observation period at Visit 1 (Day -29 to Day -1 before the start of study drug administration)
4. Patients who, in the opinion of the principal investigator or the investigator, are capable of understanding the content of the clinical study and complying with the study protocol requirements.
5. Patients who can provide written informed consent prior to the conduction of the clinical study procedures.
6. Patients aged ≥ 20 years at the time of informed consent

[Rationale for the inclusion criteria]

1. These patients were subjected in the clinical study because omega-3-acid ethyl esters is indicated for “hyperlipidemia.”
2. This was set so that the lipid and lipoprotein profile in the blood may be investigated in detail when omega-3-acid ethyl esters is added to a HMG-CoA reductase inhibitor. Change in the dose regimen of the HMG-CoA reductase inhibitor is not allowed during the study, so that efficacy may be assessed accurately.
3. The lower limit was set according to the diagnostic criteria for hypertriglyceridemia in “Japan Atherosclerosis Society (JAS) Guidelines for Prevention of Atherosclerotic Cardiovascular Diseases 2012.” The upper limit was set as using a reference in the clinical settings when adding omega-3-acid ethyl esters to a HMG-CoA reductase inhibitor.
4. 5. These were set as fundamental items for the study.
6. Patients should be ≥ 20 years of age, so that they may make up their mind to participate in the study at their own discretion.

7.2 Exclusion criteria

Study subjects meeting any of the criteria below shall not be included in this study.

1. Patients who had clinically significant hemorrhagic disorders (e.g., hemophilia, capillary fragility, gastrointestinal ulcer, urinary tract hemorrhage, hemoptysis, and vitreous hemorrhage) within 24 weeks prior to the start of observation period (Day -29 to Day -1 before the start of study drug administration), or those who concurrently have the above disorders
2. Patients who had thyroid disorders (hyperthyroidism or hypothyroidism) within 24 weeks prior to the start of observation period (Day -29 to Day -1 before the start of study drug administration), those who concurrently have the above disorders, or those who are orally receiving a therapeutic drug for thyroid disorder.
3. Patients in whom the type of HMG-CoA reductase inhibitors was changed within 12 weeks prior to the start of observation period (Day -29 to Day -1 before the start of study drug administration)
4. Patients who have received an EPA preparation or an EPA/DHA preparation (including supplements) within 12 weeks prior to the start of observation period (Day -29 to Day -1 before the start of study drug administration)
5. Patients who have started antidiyslipidemic agents within 4 weeks prior to the start of observation period (Day -29 to Day -1 before the start of study drug administration)
6. Patients with severe hepatic impairment (e.g., Child-Pugh classification C)
7. Patients who were previously diagnosed as lipoprotein lipase deficiency or apoprotein C-II deficiency.
8. Patients who are concurrently having Cushing's syndrome, uremia, systemic lupus erythematosus (SLE), or serum dysproteinemia.
9. Diabetic patients who are currently receiving thiazolidine or insulin.
10. Patients who are concurrently having hypertension of grade III^{Note 1}).

Note 1: Patients with systolic blood pressure of ≥ 180 mm Hg or diastolic blood pressure of ≥ 110 mm Hg regardless of treatment with antihypertensive drugs.

11. Patients who are habitual drinkers drinking an average of over 100 mL per day (expressed in terms of quantity of alcohol), or patients with or with a history of drug abuse or addiction.
12. Pregnant, lactating or postmenopausal women.

13. Patients with a history of hypersensitivity or allergy for omega-3-acid ethyl esters.
14. Patients participating in other clinical studies
15. Patients assessed ineligible in the study by the principal investigator or the investigator

Note 2: Alcohol conversion table (reference)

Alcohol	Type	Alcohol content	Amount corresponding to 100 mL alcohol
Brewage	Sake	15%	670 mL (approx. 3 cups)
	Beer	5%	2,000 mL (approx. 3 large bottles)
	Sparkling liquor	5%	2,000 mL
	Wine	12%	830 mL
	Chinese rice wine	18%	560 mL
Distilled liquor	Ko-ruì Shochu	35%	290 mL
	Otsu-ruì Shochu	25%	400 mL
	Whiskey	40%	250 mL (approx. 3 doubles)
	Brandy	40%	250 mL (approx. 3 doubles)
	Vodka	40%	250 mL (approx. 3 doubles)
Mixed liquor	Plum wine	13%	770 mL
	Synthetic sake	16%	630 mL

[Rationale for the exclusion criteria]

- 1.13. The product is contraindicated for these patients.
2. Lipids and lipoproteins in the blood may be affected by thyroid disorders and the therapeutic drugs.
- 3.4.5. Efficacy may not be assessed accurately in these patients.
- 6.10. These were set to ensure safety of the study subjects.
7. Patients who genetically produce less lipoprotein and apoprotein should be excluded.
8. Patients with underline diseases commonly seen with secondary hypertriglyceridemia should be excluded.
9. Production of hepatic lipid parameters including TG may not be assessed accurately in these patients.
11. These were set to ensure safety of the study subjects and accurate efficacy assessment.
12. For the product, safety has not been established for the use during pregnancy, and the product should preferably not be administered to lactating women. In addition, production of lipid parameters including TG may be affected by estrogen, a female hormone.
- 14.15. These were set as fundamental items for the study.

CONFIDENTIAL

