9.1.9 Laboratory tests and the specific 20-lipoprotein fraction assay

According to the observation schedule (Appendix A), samples are to be collected in each study site for the following laboratory tests and the specific 20-lipoprotein fraction assay. The fasting test is to be performed under ≥ 10 -h fasting.

The principal investigator or investigator shall evaluate and keep the reported laboratory test results. Results of the specific 20-lipoprotein fraction assay shall be assessed by the chair and member of the Clinical Study Steering Committee.

Table 9.a Laboratory tests

Hematology^(a)	Serum chemistry^(a)
Platelet count	Total cholesterol, TG, HDL-C, LDH, AST, ALT, ALP, γ -GTP, CK(CPK)
Specific 20-lipoprotein fraction^(b), lipid content of each lipoprotein fraction^(b), mean particle size of LDL^(b), mean particle size of HDL^(b)	
Apoprotein, remnant lipoprotein	
Apolipoprotein A1 ^(a) , A2 ^(a) , B ^(a) , B-48 ^(a) , B-100 ^(c) , C-II ^(a) , C-III ^(a) , C-II/III ^(a) , E ^(a) , RemL-C ^(a)	
Others	Fatty acid fraction in total lipids^(a)
Lipoprotein lipase ^(c) , high-sensitive CRP ^(a)	24-fatty acid fraction, T/T, EPA/AA

(a) To be measured in PPD [redacted]

(b) To be assayed for the sub-class⁽⁶⁾ specified for each fraction number using HPLC in CCI [redacted] PPD [redacted]

Fraction No.	1	2	3	4	5	6	7	8	9	10	11	12	13	14	15	16	17	18	19	20
Particle diameter	>90	75	64	53.6	44.5	36.8	31.3	28.6	25.5	23	20.7	18.6	16.7	15	13.5	12.1	10.9	9.8	8.8	7.6
Sub-Class	Chylomicrons		large VLDL			medium VLDL	small VLDL	large LDL	medium LDL	small LDL	very small LDL			very large HDL	large HDL	medium HDL	small HDL	very small HDL		

(c) To be measured in PPD [redacted]

The principal investigator shall keep laboratory test reference values including the historical data with the exception of the specific 20-fraction assay using CCI [redacted]

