9.1.12 Record of study subjects who are withdrawn before randomization

A CRF shall be created for all study subjects who have signed the consent form and withdrawn before randomization.

The following items are to be described on the CRF.

- Date of consent obtainment
- Date of birth
- Gender
- Eligibility
- Adverse events (with details, if any)
- Reason for discontinuation

The primary reason for withdrawal before randomization shall be recorded on the CRF according to the following classification:

- Adverse events
- Not satisfying at least one of the inclusion criteria or meeting any of the exclusion criteria
- Major protocol deviation
- Lost to follow-up
- Voluntary discontinuation (specify the reason)
- Study termination
- Pregnancy
- Others (specify the reason)

Study subject ID codes assigned to study subjects withdrawn from the study before randomization shall not be reused.

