9.1.13 Record of randomization

Study subjects to be randomized shall meet all of the inclusion criteria and shall not meet any of the exclusion criteria according to 8.2 Section 8.2. The principal investigator or investigator shall specify the primary reason why the study subject cannot be randomized.

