9.3.2 Treatment period (Visit 2)

In consideration of the results of tests and observation at Visit 1 (Day -29 to Day -1 before the start of study drug administration), the principal investigator and the investigator shall perform the following tests, observations, and evaluations for each study subject.

Items to be checked: Food and drink consumption before visit

- Confirm that alcohol was not consumed from 9:00 pm 2 days before the visit and food was not consumed from 9:00 pm the day before the visit
 - Confirm that excessive eating/drinking and extreme change in dietary content were not made on the day before the visit.
-
- Physical examination
 - Vital signs
 - Concomitant drugs
 - Concurrent disease
 - Laboratory tests

The principal investigator or the investigator shall give notification to the Registration Center (accessing to the Case Registration Web System) regarding study subjects in whom all the tests, observation and evaluation at Visit 2 (Day -15 to Day -1 before the start of study drug administration) have been completed and study drug administration was considered possible.

The principal investigator or the investigator shall prescribe the study drug at a dose notified from the Registration Center and tell the study subject to take the drug starting from the next day.

Refer to Section 9.1.11 for preparation of records relating to the study subjects withdrawn before randomization.

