Appendix A Schedule for Study Procedures

Visit timing	Week	Screening period	Treatment period			Discontinuation ^(e)
	Day	-4	0	4	8	
Window (day)		-29 to -1	-15 to -1	14 to 41	42 to 70	Within 3 days after the last dose
Visit No.		1	2	3	4	
Informed consent		X				
Inclusion/exclusion criteria		X				
Demographic data, medical history, previous treatment drug(s)		X				
Physical examination		X	X	X	X	X
Height		X				
Body weight		X				
BMI		X				
Vital signs		X	X	X	X	X
Concomitant drugs ^(a)		X	X	X	X	X
Concurrent disease		X	X			
Laboratory tests						
Hematology/ Serum chemistry		X ^(c)	X	X	X	X
Specific lipoprotein fraction assay ^(b)		X ^(c)	X	X	X	X
Lipoprotein assay ^(b)		X ^(c)	X	X	X	X
Mean particle diameter of LDL/HDL ^(b)		X ^(c)	X	X	X	X
Fatty acid fraction in total lipids		X ^(c)	X	X	X	X
Others		X ^(c)	X	X	X	X
Study drug prescription			X	X		
Treatment compliance				X	X	X
Food and drink consumption before the visit			X	X	X	X
Evaluation of adverse events			←X→	←X→	←X	←X

(a) All concomitant drugs will be recorded.

(b) By HPLC

(c) To be performed before the Visit 2 tests

(d) Medication will be started the day after the completion of all the tests of Week 0. The start date of medication will be referred to as Day 1.

(e) To be performed to the extent possible

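### Pregnancy must be excluded before randomization, but the protocol requires no pregnancy test before allocation

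*Protocol*

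**What the plan says.** Section numbers are those in the body of the protocol; the table of contents numbers some parts of 9.1 differently.

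- **The exclusion.** Section 7.2, item 12, bars "Pregnant, lactating or postmenopausal women". The rationale below the list says that "safety has not been established for the use during pregnancy" and adds that estrogen may affect lipid parameters.
- **When it must hold.** Section 7.0 says the investigator "shall check for all the inclusion/exclusion criteria including the test results prior to randomization". Section 9.1.13 says that subjects to be randomized "shall meet all of the inclusion criteria and shall not meet any of the exclusion criteria". Under Section 9.3.2 the Registration Center is notified only of subjects who have finished the Visit 2 assessments and in whom "study drug administration was considered possible".
- **Pregnancy is foreseen at this stage.** Section 9.1.12 states: "The primary reason for withdrawal before randomization shall be recorded on the CRF according to the following classification". Pregnancy is one of the listed reasons.
- **What is measured.** The serum chemistry list in Table 9.a begins "Total cholesterol, TG, HDL-C, LDH, AST, ALT, ALP" and ends with γ-GTP and CK. The rest of the table covers platelets, lipoprotein fractions and particle sizes, apoproteins, RemL-C, lipoprotein lipase, high-sensitivity CRP and fatty acids. Appendix A schedules these under rows such as "Hematology/ Serum chemistry".
- **Other provisions on pregnancy.** Section 9.1.10 requires contraception and counselling from consent. Section 7.5, item 6, and Section 9.1.11 cover discontinuation, handover to the obstetrician and reporting once a pregnancy is known.

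**The concern.** The protocol sets a condition for randomization and names no procedure capable of establishing it. An early pregnancy can be unknown to the woman and invisible on physical examination. Contraception that starts at consent cannot exclude a pregnancy that began before consent.

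What is at stake is participant safety. A pregnant woman could be randomized to omega-3 and take 4 g/day, with up to 8 weeks of treatment planned, until the pregnancy came to light by other means. She would be an ineligible randomized subject under Section 9.1.13 even though the site had made no error. The discontinuation and reporting rules limit the length of exposure but do not prevent it.

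**Working it through.** The plan gives no figure to reproduce, so the check is a reading of every place where a test could be required, set against the places that require the condition to hold.

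**Step 1: is absence of pregnancy required at randomization?** Yes. Sections 7.0 and 9.1.13 both say so, and Section 8.3 places allocation at the start of the treatment period, which is Visit 2.

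**Step 2: is a test required anywhere?**

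| Place | Content | Pregnancy tests |
|---|---|---|
| Table 9.a, hematology and serum chemistry | platelets (1) + chemistry (9) = 10 items | 0 |
| Table 9.a, remainder | fraction assay and particle sizes (4) + apoproteins and RemL-C (10) + lipoprotein lipase and CRP (2) + fatty acids (3) = 19 items | 0 |
| Sections 9.3.1 to 9.3.4 | Visits 1 to 4 | 0 of 4 visits |
| Appendix A | all rows | 0 |

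Table 9.a thus lists 10 + 19 = 29 items, none of them hCG. The item count depends on how panels are split, but the zero does not. The Appendix A row headed Others corresponds to lipoprotein lipase and CRP in Table 9.a. Redaction does not account for the gap: what is blacked out in that table is where assays are run and an assay name, while the analytes are legible. The SAP laboratory variables and listings contain no pregnancy test either.

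**Step 3: do the remaining provisions fill the gap?**

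- Contraception from consent acts forward only. Estrogen and progestogen are prohibited from Visit 1 to Visit 4 (Section 7.3.1), which restricts hormonal methods, and the protocol text does not define what counts as adequate.
- Physical examination, concurrent-disease review and investigator judgement at Visit 2 can catch an evident pregnancy, but they are not reliable for an early one.
- Section 7.5 and Section 9.1.11 operate only after detection.

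**Step 4: whom does it concern?** As written, item 12 also excludes postmenopausal women. Women who enter should therefore be premenopausal and, unless sterilized, of childbearing potential. Section 9.1.10 expressly expects such women.

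**Step 5: when should status be checked?** Appendix A marks the eligibility check at Visit 1 only. Visit 1 may fall as early as Day -29 and Visit 2 as late as Day -1, an interval of up to 29 - 1 = 28 days. Status can change over that time, so a test at Visit 1 alone would not be enough.

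**Step 6: how many exposures?** Expected exposures would be the number of women of childbearing potential allocated to omega-3 (at most 25 among the planned evaluable patients), times the probability of an unrecognised pregnancy at Visit 2. The documents give neither the number of such women nor that probability, so no estimate is offered.

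**The case against.** The strongest reply is that this is a design choice of low consequence. Nothing in the protocol prescribes a laboratory method for each criterion, and several other exclusions (bleeding disorders, thyroid disease, Cushing's syndrome, SLE, alcohol intake) also have no dedicated test. The drug is marketed, the regimen is the approved one (Section 6.2), treatment lasts 8 weeks, and half of the planned subjects receive no study drug. Women of childbearing potential sign consent only after counselling on contraception. Visit 1 is nominally four weeks before treatment, which gives many pregnancies time to become apparent, and examination is repeated at Visit 2. Exclusion 15 lets the investigator decline anyone in doubt, and a site may run its own test.

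Part of this stands. There is no internal contradiction, the documents show no known fetal hazard, and the number affected is probably small. Listing pregnancy as a reason for withdrawal before randomization also shows that sites are expected to look for it.

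The rest does not close the gap. The four-week interval is nominal: the Visit 1 window runs to Day -1. A discretionary test is not a required one. The comparison with other exclusions is weak, because those conditions are usually known from the history, whereas an early pregnancy may be unknown to the woman herself. Ordinary prescribing of the drug is not the standard either, since this protocol chose to exclude pregnancy and to require verification before randomization.

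**Conclusion.** The concern holds. Absence of pregnancy is a condition of randomization, and no test at any of the 4 visits, nor any of the 29 items in Table 9.a, would establish it. A fully compliant site could dose a woman with an unrecognised early pregnancy.

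This should be corrected as a matter of participant safety and eligibility verification. It does not affect the primary analysis, alpha or power. The number of exposed pregnancies is unknown and probably small, and the stated ground for the exclusion is that safety is not established, not that harm is known. The conclusion assumes that no separate required procedure exists outside the two documents. Consent pages were not available, but a mandatory test would be expected in Table 9.a, Section 9.3 or Appendix A.

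**What to change.** For women of childbearing potential, add a urine or serum hCG test at Visit 2, done the same day, with a negative result recorded before the Registration Center is notified. The edits are one row in Table 9.a, one row in Appendix A and one line in Section 9.3.2. Visit 2 is the right place because it immediately precedes allocation, and Sections 8.1.1 and 9.3.2 have dosing start the following day.

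The test precedes allocation, so candidates for both arms need it. For the planned evaluable patients the ceiling is 50 × 1 = 50 tests, reached only if every one were a woman of childbearing potential; the true number is lower but not given. Candidates tested at Visit 2 who are then not randomized or not evaluable would add a few. No extra visit is needed, and blood is already drawn at Visit 2. The documents give no unit cost.
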